
15.1 Institutional Review Board (IRB) or Ethics Committee (EC) Review
	
The protocol and the proposed informed consent form (and assent, if applicable) must be reviewed and approved by a properly constituted IRB/EC before study start. Each investigator must provide the Sponsor or its designee a signed and dated statement that the protocol and informed consent (and assent, if applicable) have been approved by the IRB/EC for that site before consenting patients. Prior to study initiation, the investigator is required to sign a protocol signature page confirming agreement to conduct the study in accordance with this protocol and to give access to all relevant data and records to the Sponsor, its designee, and regulatory authorities as required.
	
Updated for inclusion of assent.

15.3 Written Informed Consent
	
For adolescent patients, informed consent will be obtained from the parent(s) or legal guardian in accordance with regional laws or regulations. In addition, dependent upon the patient’s age and IRBs, IEC, and/or local legal requirements, assent of the patient must also be obtained. Adolescent patients may be asked to personally sign and date either a separately designed, written assent form, or the written informed consent.
	
Updated for inclusion of assent.

15.6 Protocol Deviations
	
Deviations will be reported, evaluated, and discussed according to the Protocol Deviation Plan and in the final study report.
 
All protocol deviations due to the impacts of COVID-19 will be identified and documented accordingly by the site and the Sponsor. When visits are completed remotely (due to COVID-19 or other reasons), sites should ensure the completion of at least those assessments listed in Appendix 1 Section 4. Where these study procedures are completed remotely, any additional study procedures that cannot be completed will be
	
Added language from the COVID-19 Appendix within the Protocol.

Section	Version 6	Rationale
	
noted as missing and will not be considered as a protocol deviation. The failure to complete the minimally required procedures outlined in Appendix 1 Section 4, will be considered a protocol deviation.
	

Appendix 1, Section 2: COVID-19 Infected Patients and Study Drug Use
	
If a patient enrolled in the study tests positive for Severe Acute Respiratory Syndrome Coronavirus 2 (SARS-CoV-2), <del>the causative agent of COVID-19, IP study drug</del> must be temporarily discontinued <del>until</del> The Sponsor must be notified immediately for additional guidance.
 
Study drug may be resumed when the patient no longer presents an active infection, (defined as resolution of symptoms or a negative SARS-CoV-2 test), as assessed by the Investigator and/or the patient’s physician(s). The Sponsor must be notified immediately for additional guidance. If COVID-19 symptoms persist (e.g., loss of taste or smell), the patient should be encouraged to repeat SARS-CoV-2 testing in order to minimize the duration of study drug interruption.
 
Instructions on resuming study drug following a positive SARS-CoV-2 test result COVID-19 infection are provided in Appendix 1 Section 5.5.
	
Added emphasis that Sponsor must be contacted immediately for guidance.
 
Clarified when study drug may be resumed.
 
Added language to permit sites to re-test a patient whose symptoms persist, to determine whether to re-start study drug based on the negative test, rather than resolution of all symptoms.

Appendix 1, Section 5.1: Dose Escalation Period
	
<del>The first 8 weeks of the trial require intense safety monitoring of patients as they progress through the dose escalation period of the study. Because in person clinical visits may not be feasible, patients who are in the dose escalation period of the study should remain on their current IP dose. The dose at the last in-person clinic visit, if not the goal dose, will be considered the maximum dose until completion of dose escalation can be safely resumed (see Appendix 1 Section 5.5).</del>
 
<del>Protocol specified in clinic follow up visits, for safety/tolerability, must be completed where possible. Required assessments for patients who are unable to have an in person visit are described in Appendix 1 Section 4.</del>
 
Refer to Section 9.11.1.
	
Section moved.

Appendix 1, Section 5.2: Week 8-12 Visits
	
<del>Patients in the maintenance period of the trial who have completed dose escalation and who have not reached the Week 12 time point must be assessed at Week 12 by conducting an in-clinic visit, per protocol.</del>
	
Section moved.

Section	Version 6	Rationale				
	
Patients who are unable to return to the clinic/site for a scheduled Week 12 follow up visit should remain on their current IP dose and have remote assessments completed to evaluate assess safety/tolerability. —            Refer to Section 9.11.2.
					

Appendix 1, Section 5.3: Post-Week 12 Visits
	
Patients who have completed dose escalation and who have completed the Week 12 Visit must be assessed at their next scheduled visit (Week 24). Patients who will be unable to return to the clinic/site for scheduled follow up visits should remain on their current IP dose and complete remote assessments to evaluate safety/tolerability until in-clinic visits can be resumed (see Appendix 1 Section 5.5). These remote assessments may be conducted as described in Appendix 1 Section 4.            Refer to Section 9.11.3.
	
Section moved.
				

Appendix 1, Section 5.4: Dose Escalation and Interruption for Missed Safety and Laboratory
	
If no in-clinic visit is completed and remote assessments/laboratory samples cannot be collected within the per protocol allowed time window for that visit, the IP dose must be de-escalated to the previous dose within 6 days of the protocol visit window. For patients on 5 mg, the lowest dose, the dose may be maintained and no de-escalation is required. All efforts should then be made to collect laboratory samples. However, if laboratory samples cannot be collected within 14 days from the date of dose de-escalation (for visits through Week 12) and within 28 days (for visits beyond Week 12), IP must be temporarily discontinued until safety lab values can be evaluated and it is deemed appropriate to restart. Appendix 1 Section 5.5 describes the procedure for resuming and dose-escalating IP following drug interruption.            Refer to Section 9.11.4.
	
Section moved.
				

Appendix 1, Section 5.5: Resuming or Dose-Escalating Study Drug after Interruption or Changes
	
When the investigator deems it is safe for the patient to return to the site for an in-person visit, the investigator should conduct an evaluation to determine whether the patient is still eligible to receive IP and to determine the appropriate dose. This should include a confirmation that the reason for discontinuation was not a per protocol specified reason and that the patient's circumstances have not changed in a manner that would prohibit administration of the investigational drug (e.g. the patient is now taking an excluded medication). Once the investigator determines IP administration is appropriate, dosing may proceed as recommended in the table below:
 
  
 IP Status	Dosing Recommendation	
   
  	 	
  
	IP Status	Dosing Recommendation			
Section moved.

IP Status	Dosing Recommendation					

Section	Version 6		Rationale
	<del>IP temporarily discontinued for any reason (e.g., COVID-19, delays in obtaining safety lab, AEs)</del>	<del>Resume IP at last administered dose</del>	
	<del>IP dose not escalated as required per COVID-19 mitigation plan</del>	<del>Continue last administered dose; consider escalating dose, if appropriate</del>	
	<del>IP de-escalated for any reason (e.g. due to delays in obtaining safety labs, AEs)</del>	<del>Continue last administered dose; consider escalating dose, if appropriate</del>	
	
<del>If the patient is not at the target dose, dose escalation to a higher dose is permitted. Patients who dose-escalate must have a telephone call 1 week after dose escalation and an office visit (or unscheduled visit, if necessary) 2 weeks (<math>\pm</math> 3 days) after dose escalation to collect clinical chemistry, BNP, and NT-proBNP. Unscheduled visits due to dose escalation should also include assessments detailed in Section 9.7 of the protocol. Once the target dose has been reached and 2-week follow up completed, the Schedule of Assessments may be resumed.</del>
 
Refer to Section 9.11.5.
		
Appendix 1, Section 6: Deviations	
<del>Any study procedures that cannot be conducted remotely will be noted as missing. All deviations due to the impacts of COVID-19 will be identified and documented accordingly by the site and the Sponsor. The failure to complete a protocol visit will not be considered as a reason for study discontinuation and will not be considered as a major deviation. Deviations will be reported, evaluated, and discussed according to the Protocol Deviation Plan and in the final study report.</del>
 
Refer to Section 15.6.
		Section moved.
Appendix 1, Section 7: Monitoring	
<del>In case that study sites are closed for any visitors and monitors over a certain period of time during the COVID-19 pandemic a risk based approach to monitoring will be taken, focusing on certain sites, certain data points and certain processes that are critical to ensure the rights, safety and well-being of trial participants and the integrity of the trial (and trial data). The results of adjusted monitoring/review measures and their impact will be reported to the Sponsor in monitoring reports and in the clinical study report, where applicable. Adjusting monitoring activities may include a combination of on-site and off-site monitoring. Remote source data verification may also be taken into consideration.</del>
 
Refer to Section 13.1.
		Section moved.

**AMENDMENT CHANGE DOCUMENT  
CLINICAL STUDY PROTOCOL 402-C-1808**

**Study Title: A Phase 3 Trial of the Efficacy and Safety of Bardoxolone Methyl in Patients with Autosomal Dominant Polycystic Kidney Disease**

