### 7.2. Number of Patients

Approximately 850 patients will be enrolled.

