## 12. STATISTICS

### 12.1. Sample Size

With 850 patients enrolled, the study will have approximately 80% power to detect a difference between the two treatment groups in change from baseline eGFR of 2.3 mL/min/1.73 m^2. The power calculation was based on a 2-sample t-test as an estimate for the planned ANCOVA analysis and assumes the following:

- Overall two-sided Type I error rate total of 0.05;
- Standard deviation of change from baseline in eGFR of 12 mL/min/1.73 m^2;
- Analyses are based on the intent-to-treat (ITT) population;
- Missing data will be imputed using multiple imputation.

ANCOVA analysis is expected to have approximately the same power as the t-test used for study planning. The method for maintaining strict control of the Type I error for the trial will be described in the statistical analysis plan (SAP). Appropriate sensitivity analyses of the primary analysis will be specified in the SAP.

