12.3.1. Analysis of Efficacy	
The ITT population, which includes all patients randomized within each cohort, will be used as the population for assessment of the efficacy endpoints. This includes patients on tolvaptan who have already enrolled under Version 2 of the protocol.
 
Analysis of covariance (ANCOVA) will be used to analyze the primary <del>and key secondary</del> efficacy endpoints of change from baseline in off-treatment eGFR. The model will include change from baseline in eGFR as the dependent variable, treatment group as fixed effect, and baseline eGFR as continuous covariate. Other covariates may be specified in the SAP. The off-treatment endpoints assess the preserved drug benefit relative to placebo following withdrawal of treatment; therefore, analyses of these endpoints do not include eGFR values collected during treatment. <del>Missing data are not imputed.</del> Sensitivity analyses, including a tipping point analysis, will be performed to assess the impact of missing data.
	
Clarification

13.1 Study Monitoring	
In case that study sites are closed for any visitors and monitors over a certain period of time during the COVID-19 pandemic, a risk-based approach to monitoring will be taken, focusing on certain sites, certain
	
Added language to clarify adjustments in monitoring due to

Section	Version 6	Rationale
	
data points and certain processes that are critical to ensure the rights, safety and well-being of trial participants and the integrity of the trial (and trial data). The results of adjusted monitoring/review measures and their impact will be reported to the Sponsor in monitoring reports and in the clinical study report, where applicable. Adjusting monitoring activities may include a combination of on-site and off-site monitoring, where permitted by local regulations. Remote source data verification may also be taken into consideration, where permitted by local regulations.
	
COVID-19 impacts on site operations.

14.4 Investigational Documentation
	
 
The IRB- or EC-approved informed consent; (and assent, if applicable), samples of site advertisements for recruitment for this study, and any other written information regarding this study that is to be provided to the patient or legal guardians;
 
	
Updated for inclusion of assent.

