Section 8.1 Patient Inclusion Criteria	3. Screening eGFR (average of Screen A and Screen B eGFR values) $\geq 30$ <del>and</del> to $\leq 90$ mL/min/1.73 m  (18 to 55 years) or $\geq 30$ <del>and</del> to $\leq 44$ mL/min/1.73 m  (56 to 70 years): a. Patients with either screening eGFR <math>\geq 60</math> to <math>< 90</math> mL/min/1.73 m^2 or age 56 to 70 years, must have evidence of ADPKD progression (i.e., eGFR decline of <math>\geq 2.0</math> mL/min/1.73 m^2 per year, based on historical eGFR data and medical monitor discretion); b. The two eGFR values collected at Screen A and Screen B visits used to determine eligibility must have a percent difference $\leq 25\%$ ;	Added requirement for evidence of ADPKD progression to ensure the population studied in the trial is one that is at risk of progression to ESKD
Section 8.1 Patient Inclusion Criteria	6. Adequate bone marrow reserve and organ function at the Screen A visit as follows: a. Hematologic: Absolute neutrophil count $> 1.5 \times 10^9/L$ , platelets $> 100 \times 10^9/L$ , hemoglobin (Hgb) $\geq 9$ g/dL; b. Hepatic: Total bilirubin (TBL) $\leq 1.5X$ <del>the upper limit of normal (ULN)</del> , alanine aminotransferase (ALT), and aspartate aminotransferase (AST) $\leq$ <del>the upper limit of normal (ULN)</del> 1.5X ULN ;	Changed upper limit to require within normal limits
Section 8.1 Patient Inclusion Criteria	10. Concomitant use of tolvaptan during the study is permitted if the following criteria are met: a. Patient must have been receiving tolvaptan for at least 6 months prior to Screen A visit; b. Patient must be receiving stable dose of tolvaptan for at least 8 weeks prior to Screen A visit; c. ALT and AST must be within normal limits ( $\leq$ ULN) at Screen A visit; d. Patient has no history of elevations of ALT or AST $>$ ULN while receiving tolvaptan; e. Tolvaptan dose is not expected to change or be stopped during the trial.	Added to inclusion requirements for patients currently receiving tolvaptan

Section	Version 2	Rationale

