7.5.1. Historical eGFR

To characterize disease progression prior to trial entry, up to 5 years of historical serum creatinine values are collected for each patient as part of their medical history. Collection of historical serum creatinine is subject to availability of data from medical records; therefore, the number of available values will vary by patient and some patients may have no historical values. Historical serum creatinine values are converted to mg/dL and eGFR is calculated for analysis according to the appropriate equation (Section 6.5.4) using the patient age at laboratory collection for adult patients, or patient height at Screening for adolescent patients. Historical serum creatinine values were analyzed at various local laboratories (i.e., not collected as part of central lab data). Therefore, historical serum creatinine and corresponding eGFR values are considered part of a patient's medical history, and distinct from central lab assessments collected as part of the trial.

The eGFR values used in the analysis dataset for the baseline label (Table 8) are the baseline eGFR values for each patient (defined in Section 6.4.2), not the individual Screen A, Screen B, and Day 1 eGFR values.

Historical values are prior to first dose and have a negative Study Day value:

- $\text{Study Day} = (\text{Date of Historical Lab Collection}) - (\text{Date of Screen A})$

Summary statistics of eGFR results by historical year (listed in Table 8) will be presented for the ITT population. Summary statistics of available historical eGFR results are based on the following analysis windows:

Table 8: LABELS FOR SUMMARY OF HISTORICAL CHANGE IN eGFR

Analysis Visit	Label	Study Day Windows
-5	Historical Year 5	1825 to 1461 days prior to Screen A
-4	Historical Year 4	1460 to 1096 days prior to Screen A
-3	Historical Year 3	1095 to 731 days prior to Screen A
-2	Historical Year 2	730 to 366 days prior to Screen A
-1	Historical Year 1	365 to 1 days prior to Screen A
0	Baseline	Screen A to Day 1

The summary statistics will include the average eGFR value by patient and analysis time point. For instance, if multiple values are listed in the historical Year 1 results for a given patient, the average of those values is used to calculate the summary statistics.

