8.4. Primary Endpoint

8.4.1. Primary Endpoint Analysis

The primary endpoint of this study is the off-treatment change from baseline in eGFR at Week 108. The ITT population will be used for all analyses. For all patients enrolled in the trial, Week 108 is the off-treatment eGFR assessed closest to 108 weeks after Study Day 1. For a patient who completed 2 years of treatment, the 8-week drug treatment withdrawal period occurs at Week 108 (i.e., 56 days after last dose). For a patient who stopped drug treatment early, the eGFR assessment at Week 108 is analyzed, irrespective of how long a patient has been off-treatment. Analysis of Week 108 (after a planned 8-week drug treatment withdrawal period) assesses the preserved drug benefit (relative to placebo) following withdrawal of treatment.

The off-treatment change from baseline eGFR at Week 108 for patients treated with bardoxolone methyl is compared to placebo using an ANCOVA model, with BASE_eGFR as a covariate, and TRT as fixed effects. The ANCOVA analysis uses eGFR values collected in the Week 108 analysis window (Section 6.5.2), which includes the follow-up assessment at Week 108 for patients who discontinued treatment early irrespective of time after last dose.

Missing Week 108 eGFR data will not be imputed.

The difference between bardoxolone methyl and placebo in change from baseline of eGFR is estimated along with the 95% confidence interval at Week 108.

Example SAS code as follows:

```
proc glm data=efficacy;
  class TRT ACR_STRAT;
  model DELT_eGFR=trt ACR_strat base_egfr /solution;
  lsmeans trt / diff stderr pdiff cl alpha=0.05;
run;
```

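### The Week 108 ANCOVA leaves out baseline age and past eGFR decline, at a small cost in precision to what is now a descriptive comparison

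*Protocol*

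**What the plan says.** Protocol 12.3.1 specifies an ANCOVA of change in eGFR on treatment and continuous baseline eGFR, and leaves any further covariates to the SAP. The Version 6 change table has the same sentence: "The model will include change from baseline in eGFR as the dependent variable, treatment group as fixed effect, and baseline eGFR as continuous covariate".

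SAP 8.4.1 repeats the model. The off-treatment change at Week 108 "is compared to placebo using an ANCOVA model, with BASE_eGFR as a covariate, and TRT as fixed effects". SAP 8 and Table 9 add the tolvaptan and screening ACR strata, each only if its smaller category exceeds 20% of enrolled patients. The example code in 8.4.1 already includes the ACR stratum; the prose beside it does not. SAP 8.6.1.2 reuses this ANCOVA at Week 112. SAP 8.5.1 uses an MMRM for Week 100 with the same baseline covariate.

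Both omitted variables are in the trial data. SAP 6.4.1 defines baseline age as age at consent. On past decline, SAP 7.5.1 says: "To characterize disease progression prior to trial entry, up to 5 years of historical serum creatinine values are collected for each patient". The visible text uses these values for summary statistics only.

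The entry criteria rely on both variables. Inclusion criterion 3 (Protocol 8.1) narrows the eGFR range at age 56 to 70. It also requires an average past loss of at least 2.0 mL/min/1.73 m² per year from patients in that age band or with screening eGFR of 60 or above. The Version 2 change table gives the reason: "Added requirement for evidence of ADPKD progression to ensure the population studied in the trial is one that is at risk".

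**The concern.** The endpoint is roughly two years of eGFR change, so it should depend on how fast each patient is losing function. The protocol treats past decline as a marker of progression, and uses age to decide who must show it. Patients aged 12 to 55 with eGFR from 30 to below 60 enter with no proof of decline. A 30-year-old and a 55-year-old, both at eGFR 45, in the same arm and in the same stratum where one is used, therefore get the same fitted change.

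If age or past decline predicts the change beyond baseline eGFR, that variation stays in the residual. The interval for the Week 108 difference is then wider than it need be, and a chance imbalance between arms in these variables is not adjusted for.

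**Working it through.** **1. Reproduce the stated power.** The inputs are from Protocol 12.1 and 7.2:
- "Approximately 850 patients will be enrolled", allocated 1:1, so 425 per arm
- "Overall two-sided Type I error rate total of 0.05"
- "Standard deviation of change from baseline in eGFR of 12 mL/min/1.73 m"²
- the claim of "approximately 80% power to detect a difference between the two treatment groups in change from baseline eGFR of 2.3 mL/min/1.73 m"²

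SE = SD × √(2/n) = 12 × √(2/425) = 0.823.

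The two-sample non-central t calculation gives 79.7% power, and the normal approximation 79.8%. By the normal formula, 80% power needs 428 per arm, or 856 in total, against 850 planned. The stated figure holds. Protocol 12.1 expects the ANCOVA to have about the same power as the t-test, so it credits no covariate gain, and omitting age or slope cannot make the figure wrong.

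**2. Effect of adding covariates.** Take 12 as the residual SD before the addition. Let R² be the share of that residual variance explained by the added covariates. Then the new SD is 12 × √(1 − R²), and the SE changes by the factor √(1 − R²). The documents give no R², so every row after the first is an assumption.

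| R² | Residual SD | SE at 425 per arm | Fall in SE | 95% CI half-width | Power (non-central t) |
|---|---|---|---|---|---|
| 0 | 12.00 | 0.823 | – | 1.61 | 79.7% |
| 0.02 | 11.88 | 0.815 | 1.0% | 1.60 | 80.5% |
| 0.05 | 11.70 | 0.802 | 2.5% | 1.57 | 81.7% |
| 0.10 | 11.38 | 0.781 | 5.1% | 1.53 | 83.7% |

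The fall in SE is proportional, so it carries over to a smaller analysed sample. The SE, half-width and power columns apply only to 425 per arm with complete Week 108 data.

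**3. Is that range of R² plausible for past slope?** Day 756 is 756/365.25 = 2.07 years. Assume a between-patient slope SD of 3 mL/min/1.73 m² per year and a past-to-future slope correlation ρ. Then R² = (2.07 × 3 × ρ)²/144, which is 0.02 at ρ = 0.3 and 0.07 at ρ = 0.5. Neither the SD nor ρ is in the documents.

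**4. What happens if slope shrinks the sample.** Suppose 10% of patients lacked a usable slope and were dropped, with R² = 0.05. Power by the normal approximation would be 77.6%, below the 79.8% obtained with no added covariate. Slope helps only if every patient who would otherwise be analysed stays in. Age raises no such problem.

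**5. Which analysis this applies to.** SAP 2 records that development was discontinued and that sites were told on 10 May 2023. SAP 8.3 makes all significance levels nominal and descriptive. SAP 6.6.1 and 8.4.1 do not impute missing Week 108 values. The number of patients with a Week 108 value is not given.

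**The case against.** The case against runs as follows. The protocol permits further covariates but does not require them, and the SAP used that discretion. Randomisation makes the simpler model valid, and its interval already allows for chance imbalance. The planned power is met without age or slope. No confirmatory test remains to gain power. The size of the benefit rests on an R² that nobody has documented, and age already enters adult eGFR through the CKD-EPI equation. All of this stands, and it is why the point is minor. It does not remove the case for using a prognostic value that is already recorded.

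The objection to past slope is stronger. Under SAP 7.5.1 the historical values come from various local laboratories, vary in number, may be absent, and use Screening height for adolescents. No slope definition exists. That is enough to keep slope out of the main model.

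A reader might infer more than the documents support:
- **That the model adjusts for baseline eGFR alone.** SAP 8 brings in two strata conditionally, and the 8.4.1 code contains one of them.
- **That the two patients at eGFR 45 must have declined at very different speeds.** The documents give average rates and an entry threshold, not patient-level rates by age.
- **That the power column amounts to extra patients.** It assumes 425 per arm with complete data and a confirmatory test, and neither describes the analysis now planned.

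Parts of the SAP between 8.5.1 and 8.6.1.2 are redacted, so the criticism reaches only the visible models.

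**Conclusion.** The point holds as a minor one about precision. No visible Week 108 model contains baseline age or past eGFR decline, although the entry criteria use both to select progressing patients.

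The omission does not bias the randomised comparison, and the stated power is correct. Missing Week 108 values may raise their own questions, but the documents do not show that leaving out age makes those worse.

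Under the assumed R² of 2% to 10%, the standard error falls by about 1.0% to 5.1%. The benefit is a somewhat narrower descriptive confidence interval among patients with Week 108 data. It is not a gain in confirmatory power. Age alone might explain less than age and slope together, and nothing in the documents settles how much.

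**What to change.** Before database lock:
1. Add baseline age (SAP 6.4.1) as a continuous covariate to the Week 108 ANCOVA in SAP 8.4.1, the Week 112 ANCOVA in 8.6.1.2 and the Week 100 MMRM in 8.5.1. For the MMRM, state whether age interacts with visit, as baseline eGFR does in the example code, and where age falls in the order of terms dropped on non-convergence.
2. Make the 8.4.1 prose and example code agree on the ACR stratum, in line with the 20% rule in SAP 8.
3. Keep the current model as a sensitivity analysis.
4. If past slope is wanted, use it in a supplementary analysis only. Prespecify the slope definition, the minimum number of values, and a missing-value rule that keeps every patient who would otherwise be analysed.

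The cost is one extra model term, a sensitivity run and a few lines of SAP text and code. No new data are needed, and adding age drops no patient.
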